Clinicaltrials.gov ID: NCT03712410

Title: A Problem Solving Intervention for Hospice Caregivers

PI: [name]

Date of Document: December 20, 2022

Study Protocol and Data Analysis

Design

The study was designed as a randomized clinical trial with four groups. Hospice caregivers were randomly assigned to either to a group receiving standard hospice care with the addition of the PISCES intervention delivered face to face (Group 1) or a group receiving standard hospice care with the addition of the PISCES intervention delivered in a hybrid format (first session in person, remaining sessions via video) (Group 2) or a group receiving standard hospice care with the addition of the PISCES*plus* intervention delivered in a hybrid format (Group 3) or a group receiving standard hospice care with the addition of the PISCES*plus* intervention delivered entirely online (Group 4).

Setting and Participants

We partnered with Penn Homecare and Hospice Services. Penn Homecare and Hospice Services is an agency (part of the Penn Medicine system) that is Medicare and Medicaid-certified, accredited by the Joint Commission, licensed in the Commonwealth of Pennsylvania. It serves patients and families in Philadelphia, Chester, Delaware, Bucks and Montgomery counties mostly (total number of counties serves is 20) and is experiencing a growth over the years (20% increase in admissions over the past 5 years). The hospice component of the agency had a total number of 2,970 home admissions, an average daily census of 380 and an average length of service (LOS) of 68 days in 2016

Inclusion criteria for caregivers were the following:

- enrolled as a family/informal caregiver of a hospice patient
- 18 years or older
- with access to a standard phone line or Internet and computer access at home
- without functional hearing loss or with a hearing aid that allows the participant to conduct telephone conversations as assessed by the research staff (by questioning and observing the caregiver)
- no or only mild cognitive impairment—mental status will be assessed using the Short Portable Mental Status Questionnaire;¹ individuals with a score of less than seven (i.e., more than three errors) will be excluded, similar to other studies involving this instrument.
- speak and read English, with at least a 6th-grade education

Enrollment

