The hospice admissions staff presented the research opportunity to caregivers upon admission, asking them if they agree to be contacted by the research staff to find out more about the study. The admissions staff then forwarded contact information for caregivers willing to learn more about the study to the research team if they fulfilled the eligibility criteria. The interventionist called and scheduled the initial visit. The interventionist visited the caregiver, discussed the project, obtained informed consent from the caregiver, and documented demographic data. The interventionist opened a numbered sealed envelope, prepared by the team in advance, which assigned caregivers to one of the three groups. This approach ensured that consent is obtained prior to group assignment and caregivers consent to participate in the study, regardless of group assignment. Randomization was stratified by site. Furthermore, we followed a block randomization approach to ensure that treatment groups are not imbalanced with respect to time of the year as season (e.g., holidays) may have an effect on some of the psychometric measures. Upon consent, caregivers were asked to review and prioritize common caregiver concerns using a checklist, as the intervention will focus on the top three concerns or problems. Following this visit, a research assistant called the caregiver to conduct the baseline assessment (including anxiety, quality of life, caregiver reaction and problem solving inventory) over the phone. The research assistant was blinded to the caregiver's group assignment to

eliminate any potential bias. While the pre- and post assessments were conducted by the research assistant over the phone, the consent visit, actual intervention visits/ video-calls and exit interviews were delivered by an interventionist.

Group 1: PISCES delivered face to face

Before departing, the interventionist tentatively scheduled the upcoming three face-to-face visits for caregivers, and leave a manual on problem-solving designed for the lay audience based on “Solving Life’s Problems” by Nezu and D’Zurilla who developed the PST theoretical frameworkⁱⁱ with a special emphasis on hospice and hospice specific examples. The three intervention visits were scheduled with a suggested timeline between days 5 and 18 of the hospice admission.

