In this group the entire PISCESplus is delivered online. The first session is conducted via video and not in person (as is the case in Group 3). The agenda for the first video visit for caregivers (suggested timeline 5-7 days after hospice admission) includes an explanation of the purpose of the visit/call, and confirmation of the three specific problems that the caregiver had selected.

During the first session, the interventionist works on steps one and two of the ADAPT model of the PST, namely "Attitude" and "Defining the Problem and Setting Realistic Goals." Additionally, at the end of the first session, the interventionist will ask the caregiver to take the time until the next scheduled session to think about and identify some positive aspects of caregiving, whether these are tasks or responsibilities they enjoy, or other elements of the caregiving experience that they perceive as positive or beneficial.

During the second session (suggested timeline 11-13 days after hospice admission) which took place via video the interventionist covers steps three and four of the ADAPT model. At the end of the session the interventionist asked the caregiver to go over the benefits or positive aspects

of caregiving that they had identified and asked them to comment as to why they perceive these as positive or beneficial and whether there are ways to maximize the perceived benefits. The interventionists asked the caregiver to take the time until the next scheduled session to record how the appreciation of these positive elements helps them through stressful situations or when they have negative thoughts.

The third session (suggested timeline 16-18 days after hospice admission) which also takes place via video focuses on step five, namely trying out the solution plan and determining if it works. The interventionist concluded the session by briefly discussing the caregiver's perceived positive aspects of caregiving and reiterating the importance of recognizing and celebrating these aspects during the caregiving trajectory.

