	Video	Telephone	Video	Video	Video	Telephone	Telephone
Delivered by:	I	RA (blinded to group assignment)	I	I	I	RA (blinded to group assignment)	RA

I=Interventionist; RA=Research Assistant; F2F=Face-to-Face

Measures for Specific Aim 3

We conducted exit interviews with caregivers in all three groups. Caregivers in Group 1 were asked to provide general feedback about the PISCES intervention. Exit interviews with caregivers in Groups 2, and 3 also assessed caregivers' perceptions of the hybrid delivery platform (face to face and video sessions); caregivers in Groups 3 and 4 were further asked to provide feedback on the positive reappraisal aspects of PISCESplus. Interviews were carried out by the research coordinator and audio-taped based on an interview protocol aiming to examine caregivers' perceptions and satisfaction. Interview questions pertained to satisfaction with this form of interaction, barriers and facilitators to the use of video, and confidence in using this form of interaction, lasted 20 to 30 minutes. The interviews were digitally recorded and transcribed. The QSR Nvivo11 software was used to manage and interpret the data. This software facilitates the organization of emerging ideas, to search and explore in context, and to seek patterns.

Measures for Specific Aim 4:

We conducted a cost analysis and we utilized the demographic data collected on enrollment in the study to allow for comparisons between the groups. These include hospice admission date and diagnosis, patient and informal caregiver age and sex, race, informal caregiver employment status, education and income range, relationship of informal caregiver to patient, and residence of the informal caregiver. We also equipment costs (including equipment price and depreciation), and training costs based on time to train research staff in the use of videoconferencing. The participating hospice agency also furnished the research team with the following client-level data to estimate resource use and costs:

- direct care time for scheduled visits by type of professional
- travel distance and time spent traveling for scheduled visits by type of professional
- direct care time for after-hour calls and visits by type of professional
- travel distance and time spent traveling for after-hour visits by type of professional

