The primary analyses focused on examining differences between treatment groups in terms of caregiver outcomes during the time of intervention. Changes in caregivers’ scores from baseline to post-treatment will be analyzed using analysis of covariance, with baseline score, site, and whether the caregiver’s patient has died, as covariates. Separate models were run for each outcome (caregiver quality of life, anxiety, depression, and problem-solving ability). For Specific Aim 1 (SA1) to assess the equivalence between PISCES F2F and PISCES in hybrid format, a confidence interval approach was used on the ANCOVA model, with a two-sided 5% level of significance. If the CI of the difference between the two groups falls within the pre-specified range of equivalence, the two interventions will be considered equivalent.^{xiii xiv} The range of equivalence is defined between $-\Delta$ and $+\Delta$. The clinically informed Δ s for the primary outcomes are: CQLI-R = 1.0; GAD-7 = 1.75; PHQ-9 = 2.0; PSI = 2.5, respectively. The analyses of equivalence will be on a per-protocol basis and will be supplemented by secondary sensitivity intent-to-treat analyses.⁵⁵

The analyses for Specific Aim 2 (SA2) focus on pair-wise comparisons between PISCES*plus* and the other treatment groups. A significance level of $\alpha=0.025$ for each comparison was used to account for the multiple (2) comparisons and assure an overall significance level of no more than 0.05 for each outcome. These analyses of superiority was on an intent-to-treat basis, using

multiple imputation to address missing data. ANCOVA and chi-square tests were used to determine whether attrition had an impact on sample composition. Specifically, analyses were computed on baseline demographic characteristics, as well as baseline outcome measures, to determine whether participants who completed all phases of data collection were initially different when compared with persons who did not complete the intervention. Data were analyzed using the Stata statistical package.

Data Analysis for Specific Aim 3

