Interview sessions were audio-recorded and transcribed. Data were analyzed using a qualitative thematic coding approach. Data codes were inductively generated. Data analysis was performed by two members of the research team and validity of interpretations was checked by a third member. Transcript data were coded by line and sentence for descriptive (first-level) and theme (pattern) codes.⁶⁵ A list of major thematic elements was extracted by thorough study and coding of the interview transcripts. The analysis was organized into an expanding list of themes, arising from content, concepts, and descriptive categories (the process will be supported by the use of QSR NVivo11, an index-based qualitative analysis software package). The thematic elements was used to develop coding keywords. Each response was coded along a number of salient dimensions, such as topic, thematic content, and general sentiment using the previously abstracted keywords. Data were grouped and reviewed for trends and patterns or ideas that give insight into caregivers' overall satisfaction with the intervention, their perception of the hybrid delivery platform (for Groups 2 and 3) and of the positive reappraisal modules (for Group 3). Perceived benefits and challenges associated with both the focus and content of the intervention and its components as well as the mode of delivery were examined.

Data Analysis for Specific Aim 4

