Our cost analysis compared the three intervention groups with respect to total costs. Using the resource use and cost information, and the cost of client-specific hospitalizations and emergency department visits as described earlier, we estimated the total cost of care for each client. These data were used as the dependent variable in four pair wise regression analyses comparing the four groups with respect to total costs incurred over the study timeframe. Analysis of variance methods was employed. We also examined resource use, and compared this between groups. Specifically, we compared the number of after-hours calls and, and the number of hospitalizations and emergency department visits. As these outcome variables are each an event-count, each cannot be truly normal in distribution. Traditional regression methods assume a normally distributed outcome with constant variance. In contrast, count data are discrete and usually involve many observations with identical values and often highly right-skewed due to a few individuals with extreme event counts. We used both Poisson regression and the Zero-Inflated Poisson model for a comparison of the number of after-hour visits and calls. We also controlled for demographic covariates in these models. Direct and indirect costs for the hospice program were computed as the sum of implementation and operating costs. Intervention implementation costs included equipment costs (based on equipment price and depreciation), and staff training costs. Operating costs were measured by staff costs (wages and time) for delivery of the intervention (based on average wages and average time research staff took to do the intervention), and costs of home visits (frequency and duration) by all hospice staff as documented in the record review. Caregiver costs were based on overall informal care time (using income data gather upon admission), intervention time, any time lost from work, and out-of-pocket and travel expenditures related to caregiving as reported by the caregiver during the exit interview.

Table 1: Participant characteristics

Variable	Traditional Pisces		Online Pisces		
	Group 1 (n = 154)	Group 2 (n = 152)	Group 3 (n = 154)	Online (n = 63)	P-value
Caregiver Age [Mean (Std.)]	56.8 (12.7)	58.8 (12.8)	57.4 (12.2)	56.1 (17.2)	0.5664
Caregiver GAD 7 Score [Mean (Std.)]	6.69 (5.4)	5.74 (4.9)	6.32 (4.9)	5.85 (5.2)	0.4236
Caregiver PHQ-9 Score [Mean (Std.)]	7.54 (5.7)	6.6 (5.4)	6.99 (5.3)	6.78 (5.36)	0.5267

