Taken a job or worked additional hours to earn more money		1 (1.2%)	0 (0%)	2 (2.5%)	2 (5.7%)	
None of these apply		8 (9.8%)	4 (5.3%)	6 (7.5%)	9 (25.7%)	
Decline to Answer		4 (4.9%)	8 (10.5%)	5 (6.2%)	0 (0%)	
Selected More than 1 option		25 (30.5%)	29 (38.2%)	29 (36.2%)	8 (22.9%)	

Table 2. Comparison of 4 groups

Variable	Group 1 Mean (Std)	Group 2 Mean (Std)	Group 3 Mean (Std)	Group 4 Mean (Std)	p-value
Difference (FollowUp-Baseline) GAD-7	-2.54 (4.25)	-1.49 (4.06)	-2.27 (4.56)	-1.52 (5.12)	0.1860
Difference (FollowUp-Baseline) PHQ9	-2.69 (4.29)	-1.56 (4.19)	-1.87 (4.59)	-2.02 (4.14)	0.2752
Difference (FollowUp-Baseline) CLQI	1.14 (6.42)	0.77 (4.82)	0.27 (7.17)	1.15 (5.80)	0.6233

p-value calculated using Kruskal Wallis Test

Table 3. Comparison of Traditional PISCES vs. Online PISCES

Variable	Traditional PISCES Mean (Std)	Online PISCES Mean (Std)	p-value
Difference (FollowUp-Baseline) GAD-7	-2.04 (4.18)	-2.03 (4.74)	0.5638
Difference (FollowUp-Baseline) PHQ9	-2.15 (4.27)	-1.91 (4.44)	0.9848
Difference (FollowUp-Baseline) CLQI	0.96 (5.70)	0.54 (6.76)	0.9169

p-value calculated using Wilcoxon Two Sample Test

Table 4. Within-Group Comparison Baseline vs. Follow-up

Variable	Traditional PISCES Mean (Std)	p-value	Online PISCES Mean (Std)	p-value
GAD-7	-2.04 (4.18)	<0.0001	-2.03 (4.74)	<0.0001
PHQ9	-2.15 (4.27)	<0.0001	-1.91 (4.44)	<0.0001

CLQI	0.96 (5.70)	0.0155	0.54 (6.76)	0.0504
------	-------------	--------	-------------	--------

p-value calculated using Wilcoxon Signed Rank Test

ⁱ Pfeiffer E. A short portable mental status questionnaire for the assessment of organic brain deficit in elderly patients. *Journal of American Geriatrics Society*. 1975; 23: 433-41.

ⁱⁱ Nezu AM, Nezu CM, D'Zurilla TJ. *Solving Life's Problems: A 5-Step Guide to Enhanced Well-Being*. Springer Publishing Company: New York, 2007.

ⁱⁱⁱ McMillan SC, Small BJ, Weitzner M, Schonwetter R, Tittle M, Moody L, Haley WE. Impact of coping skills intervention with family caregivers of hospice patients with cancer: a randomized clinical trial. *Cancer* 2006; 106(1):214-222.

^{iv} Radziewicz R, Rose JH, Bowman K, Berila RA, O'Toole E, Given B. Establishing Treatment Fidelity in a Coping and Communication Support Telephone Intervention for Aging Patients With Advanced Cancer and Their Family Caregivers. *Cancer Nursing*. 2009;32(3):193-202.

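### Specific Aim 2 sets alpha at 0.025 for two comparisons, but the four-group design gives four PISCESplus-versus-PISCES pairs, and testing all four at 0.025 has an overall level of about 0.084

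*Combined protocol and SAP*

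**What the plan says.** Under Data Analysis for Specific Aims 1 and 2, Specific Aim 2 (SA2) is a set of pairwise superiority contrasts of PISCESplus against the remaining arms. Each is tested at 0.025 "to account for the multiple (2) comparisons and assure an overall significance level of no more than 0.05 for each outcome". The two contrasts are not named. Sidedness is stated for Specific Aim 1 but not for SA2.

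The Design section says "The study was designed as a randomized clinical trial with four groups". Groups 1 and 2 receive PISCES (face to face and hybrid). Groups 3 and 4 receive PISCESplus (hybrid and online). The Group 4 section confirms that "In this group the entire PISCESplus is delivered online".

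Other sections disagree on how many groups there are and which ones count as PISCESplus:

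- Enrollment describes sealed envelopes "which assigned caregivers to one of the three groups".
- Measures for Specific Aim 3 says that "caregivers in Groups 3 and 4 were further asked to provide feedback on the positive reappraisal aspects of PISCESplus".
- Data Analysis for Specific Aim 3 limits the same topics to Groups 2 and 3 for delivery format and to Group 3 alone for reappraisal: "for Groups 2 and 3) and of the positive reappraisal modules (for Group 3".
- Data Analysis for Specific Aim 4 mentions three intervention groups, then "four pair wise regression analyses comparing the four groups with respect to total costs", without listing the pairs.
- Table 3 is headed "Comparison of Traditional PISCES vs. Online PISCES" and has only two columns.

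**The concern.** The plan claims that its rule guarantees an error rate. That guarantee depends on the number of tests, and the number stated does not match the design as now described. A count of two is right for a three-group trial with one PISCESplus arm. The surviving three-group wording suggests that the count was carried over when a fourth group was added.

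As written, a reader cannot tell which SA2 tests are protected at 0.05 per outcome. A Group 4 versus Group 1 difference with p = 0.02, for instance, could be presented as confirmatory or as exploratory. The document already contains results, so an undefined family also leaves room to choose the comparisons after seeing the data.

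**Working it through.** **Inputs.** Per-test alpha 0.025, two comparisons and a claimed level of at most 0.05 come from Data Analysis for Specific Aims 1 and 2. Group sizes 154, 152, 154 and 63 come from Table 1 (Participant characteristics). Two-sided testing is an assumption, because SA2 does not state sidedness.

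**1. The plan's own figure.** 2 × 0.025 = 0.05, so the stated level is correct for two tests. For independent tests it would be 1 − 0.975² = 0.0494. Group 3 versus Groups 1 and 2 share an arm, and their correlation is (1/154) / √[(1/154 + 1/154)(1/154 + 1/152)] = 0.498. The level is then 0.046.

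**2. The count under the current design.** Two PISCESplus arms × two PISCES arms = 4 pairs: 3v1, 3v2, 4v1, 4v2.

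**3. The level for four pairs at 0.025.** The Bonferroni bound is 4 × 0.025 = 0.10. Independent tests would give 1 − 0.975⁴ = 0.0963. The pairs share arms, so the level was simulated (6 million draws) with no true differences. Group means m_i were drawn from N(0, 1/n_i), with z_ij = (m_i − m_j) / √(1/n_i + 1/n_j), and a false positive was counted if any |z_ij| exceeded 2.241. Covariates were left out. The result is 0.084.

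**4. Other readings and sensitivity.**

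| Family tested | Per-test alpha | Overall level |
|---|---|---|
| Group 3 v 1 and 2 | 0.025 | 0.046 |
| Groups 3+4 pooled (154 + 63 = 217) v 1 and 2 | 0.025 | 0.047 |
| Four pairs, enrolled sizes | 0.025 | 0.084 |
| Four pairs, equal groups | 0.025 | 0.086 |
| Four pairs, Group 4 reduced to 40 | 0.025 | 0.083 |
| Four pairs, Table 2 standard deviations | 0.025 | 0.083 to 0.084 |
| Four pairs, one-sided | 0.025 | 0.081 |
| Five pairs (adding 3v4) | 0.025 | 0.095 |
| Four pairs | 0.0125 | 0.044 |

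**5. Do the reported tables settle the family?** Weighting the Table 2 changes for Groups 3 and 4 by 154 and 63 gives:

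- GAD-7: (154 × −2.27 + 63 × −1.52) / 217 = −2.05, against −2.03 in Table 3.
- PHQ-9: (154 × −1.87 + 63 × −2.02) / 217 = −1.91, against −1.91.
- Caregiver quality of life: (154 × 0.27 + 63 × 1.15) / 217 = 0.53, against 0.54.

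Follow-up counts are not given, so exact agreement is not expected. Table 3 does appear to pool Groups 3 and 4. But it also puts Groups 1 and 2 in a single column, which makes one comparison, not two. It therefore does not supply the missing definition.

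**The case against.** The strongest reply is that the plan contains no arithmetic error. It states two comparisons, and 2 × 0.025 is 0.05. The sentence treats PISCESplus as a single comparator, and two readings fit it: Group 3 against Groups 1 and 2, or all PISCESplus participants against each of Groups 1 and 2. Both keep the level below 0.05, and the figure of 0.084 needs a family larger than the plan's own count. On this view the plan is unclear but not wrong, and the consequence is hypothetical because no SA2 test is reported.

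Much of this stands. The multiplication is correct, inflation has not been shown to occur, and 0.084 is conditional on all four pairs being tested. It is also fair that the cost analysis is weak evidence about SA2, since it concerns another aim and does not list its pairs. Nor is four the only possible larger count: reading the other arms to include the second PISCESplus arm gives five.

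The reply does not remove the problem. Stating a count without naming the tests does not define a family, and nothing in the plan excludes Group 4 from SA2 or says that Groups 3 and 4 are pooled for it. The two coherent readings differ from each other in exactly how they treat Group 4.

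**Conclusion.** The concern holds. The stated count and threshold do not fit the four-group design, and the claimed 0.05 per outcome is kept only under restrictions the plan does not state. Testing all four PISCESplus-versus-PISCES pairs at 0.025 gives about 0.084. The range is 0.083 to 0.086 over the two-sided variants tried, 0.081 if one-sided, and 0.10 as the bound. These figures assume no true differences, a normal approximation and no covariate adjustment; all but the Table 2 variant also assume equal variances.

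The mismatch itself is certain. Whether any error inflation follows depends on which tests are run. Tables 2 to 4 contain no SA2 pairwise test and no claim that PISCESplus is superior, so the problem concerns the rule and any later SA2 report. It should be fixed, but it does not overturn a result shown here.

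**What to change.** In Data Analysis for Specific Aims 1 and 2, list the SA2 comparisons, state their sidedness, say how Group 4 is handled, and match alpha to the count.

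- **Option A.** Make 3v1 and 3v2 confirmatory at 0.025 each and report Group 4 comparisons descriptively. The count of two, 0.025 and 0.05 then all stand. Neither confirmatory test loses power; what is given up is a confirmatory claim for online PISCESplus.
- **Option B.** Keep all four pairs at 0.05/4 = 0.0125 each, or use Holm over the four, and correct the count and the threshold.
- **If pooling of Groups 3 and 4 was intended for SA2,** say so there. Two tests at 0.025 then remain valid.

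Before making Group 4 comparisons confirmatory or pooling Group 4, note how it differs from the other arms in Table 1 (Participant characteristics). Bereaved caregivers are 6.4% against 28.7% to 31.5%, and a dementia diagnosis is recorded for 56.5% against 3.9% to 6.8%. The documents do not explain this.

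The text change is one or two sentences. Option B at a fixed 0.0125 costs some power. A test with an assumed 80% power at 0.025 has Φ(2.241 + 0.842 − 2.498) = 72% at 0.0125. The difference detectable with 80% power is (z + 0.842) × √(1/n₁ + 1/n₂), with z = 2.241 at 0.025 and 2.498 at 0.0125. It rises from 0.35 to 0.38 SD for 154 versus 154, and from 0.46 to 0.50 SD for 63 versus 154.

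State when the choice was made, and label it post hoc if the data had already been seen.

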Decline to Answer	2 (1.4%)	1 (0.7%)	2 (1.5%)	2 (3.2%)	
 Care Receiver Race					
Black/African American	63 (40.9%)	55 (36.2%)	50 (32.5%)	25 (39.7%)	0.7531
White/Caucasian	75 (48.7%)	84 (55.3%)	87 (56.5%)	33 (52.4%)	
Other	16 (10.4%)	13 (8.5%)	17 (11.0%)	5 (7.9%)	
 Care Receiver Marital Status					
Single/Never Married/Partnered	19 (13.2%)	18 (12.7%)	12 (9.0%)	10 (16.1%)	0.9220
Married/Partnered	57 (39.6%)	59 (41.6%)	58 (43.3%)	24 (38.7%)	
Widowed	47 (32.6%)	45 (31.7%)	49 (36.6%)	19 (30.7%)	
Separated/Divorced	21 (14.6%)	20 (14.1%)	15 (11.2%)	9 (14.5%)	
 Care Receiver Residence					
Private Home Residence/Adult Group Home	123 (84.8%)	115 (81.0%)	117 (87.3%)	54 (87.1%)	0.0488
Assisted Living Facility/Nursing Home/Skilled Nursing Facility	18 (12.4%)	22 (15.5%)	13 (9.7%)	2 (3.2%)	
Other	4 (2.8%)	5 (3.5%)	4 (3.0%)	6 (9.7%)	
 Caregiver Distance from Receiver					
With you	90 (62.0%)	72 (51.0%)	81 (60.4%)	37 (59.7%)	0.1859
Less than 1 hour away	49 (33.8%)	61 (43.3%)	42 (31.3%)	19 (30.6%)	
More than 1 hour away	4 (2.8%)	8 (5.7%)	10 (7.5%)	6 (9.7%)	
Decline to Answer	2 (1.4%)	0 (0%)	1 (0.8%)	0 (0%)	
 Caregiver Time Caring					
Less than 1 year	42 (29.0%)	46 (32.6%)	40 (29.9%)	13 (21.0%)	0.1432
1-3 years	32 (22.0%)	31 (22.0%)	28 (20.9%)	26 (41.9%)	
3 years or more	69 (47.6%)	62 (44.0%)	65 (48.5%)	22 (35.5%)	
Decline to Answer	2 (1.4%)	2 (1.4%)	1 (0.7%)	1 (1.6%)	
 Caregiver Time Spent Caring per week					
Less than 5 hours	6 (4.1%)	10 (7.1%)	7 (5.2%)	4 (6.5%)	0.7655
5-10 hours	16 (11.0%)	20 (14.2%)	12 (9.0%)	11 (17.7%)	
11-20 hours	22 (15.2%)	13 (9.2%)	20 (14.9%)	9 (14.5%)	
More than 20 hours	100 (69.0%)	96 (68.1%)	93 (69.4%)	37 (59.7%)	
Decline to Answer	1 (0.7%)	2 (1.4%)	2 (1.5%)	1 (1.6%)	
 Caregiver Added Expense					

	Yes	112 (77.2%)	104 (73.8%)	100 (74.6%)	43 (69.3%)	0.9065
	No	32 (22.1%)	36 (25.5%)	33 (24.6%)	19 (30.7%)	
	Decline to Answer	1 (0.7%)	1 (0.7%)	1 (0.8%)	0 (0%)	
Caregiver Work Status						
	Yes	61 (42.1%)	66 (46.8%)	61 (45.5%)	27 (43.5%)	0.8126
	No	83 (57.2%)	75 (53.2%)	73 (54.5%)	35 (56.5%)	
	Decline to Answer	1 (0.7%)	0 (0%)	0	0 (0%)	
Caregiver Work Support						
Cut back on hours or quit work entirely		18 (21.9%)	15 (19.7%)	16 (20.0%)	4 (11.4%)	0.1053
Taken an unpaid leave or any leave under Family Medical Leave Act		5 (6.1%)	4 (5.3%)	6 (7.5%)	1 (2.9%)	
Left one job for a different one		1 (1.2%)	3 (3.9%)	1 (1.3%)	2 (5.7%)	
Used your own sick leave or vacation time		20 (24.4%)	13 (17.1%)	15 (18.7%)	9 (25.7%)	

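### As written, the Aim 4 total-cost regressions name no site term and no baseline covariate, so cost contrasts may lose precision and those with Group 4 may mix delivery mode with case mix

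*Combined protocol and SAP*

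**What the plan says.** Data Analysis for Specific Aim 4 describes the total-cost analysis in two sentences: "These data were used as the dependent variable in four pair wise regression analyses comparing the four groups with respect to total costs", and then "Analysis of variance methods was employed". Neither names a covariate. The section next turns to event counts: "We used both Poisson regression and the Zero-Inflated Poisson model for a comparison of the number of after-hour visits and calls". The following sentence is the only one on adjustment: "We also controlled for demographic covariates in these models". It lists no variables and does not name site.

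Three other places bear on this:

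- Enrollment: "Randomization was stratified by site".
- Data Analysis for Specific Aims 1 and 2: the ANCOVA is run "with baseline score, site, and whether the caregiver’s patient has died, as covariates".
- Measures for Specific Aim 4: for the cost analysis, "we utilized the demographic data collected on enrollment in the study to allow for comparisons between the groups". The list that follows includes admission date, diagnosis, patient and caregiver age and sex, race, relationship, and the caregiver's residence, employment, education and income.

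**The concern.** Site was treated as a design factor at randomisation and in the primary models, but nothing written for Aim 4 carries it. Enrolment variables are said to serve the cost comparison, but the analysis section does not say how they enter the cost model.

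Two things are at stake. First, any cost variation that site or enrolment variables explain stays in the error term of an unadjusted comparison. Second, the participant characteristics table shows Group 4 differing from the other groups in care-receiver residence and gender. Total cost includes home visits, staff travel, and hospital and emergency use, which could plausibly depend on where and for whom care is given. At least one of the four cost contrasts must involve Group 4 if the pairs are distinct, because Groups 1 to 3 yield only three pairs. The four pairs are not named.

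A lesser point: on the natural reading, total cost is unadjusted while the count models are adjusted, so two results of one aim rest on different bases.

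**Working it through.** **1. Reproducing the printed imbalance.** Inputs are the counts in the participant characteristics table (Groups 1, 2, 3, 4), tested by Pearson chi-square without continuity correction.

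| Care-receiver variable | Counts | Printed p | Recomputed p | Groups 1–3 only | Groups 1–3 pooled vs Group 4 |
|---|---|---|---|---|---|
| Residence | private or group home 123, 115, 117, 54; facility 18, 22, 13, 2; other 4, 5, 4, 6 | 0.0488 | 0.0488 | 0.68 | 0.006 |
| Gender | male 69, 59, 69, 15; female 75, 83, 64, 47 | 0.0023 | 0.0023 | 0.22 | 0.0007 |

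The printed values reproduce, and the imbalance lies in Group 4.

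- Facility: (18+22+13)/(145+142+134) = 53/421 = 12.6%, against 2/62 = 3.2%; gap 9.4 points.
- Male: (69+59+69)/(144+142+133) = 197/419 = 47.0%, against 15/62 = 24.2%; gap 22.8 points.

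**2. Possible shift in a Group 4 cost contrast.** Shift = gap in prevalence × difference in mean cost between the categories. The documents give no cost difference, so I assume 0.2, 0.5 and 0.8 SD.

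- Facility: 0.094 × (0.2, 0.5, 0.8) = 0.02, 0.05, 0.08 SD.
- Male: 0.228 × (0.2, 0.5, 0.8) = 0.05, 0.11, 0.18 SD.

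For scale, the difference detectable with 80% power between 154 and 63 clients (two-sided 0.05) is (1.960 + 0.842) × √(1/154 + 1/63) = 0.42 SD.

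**3. Precision.** Adjustment multiplies the standard error by √(1 − R²), where R² is the share of cost variance explained. For a contrast with 80% unadjusted power, adjusted power = Φ(2.802/√(1 − R²) − 1.960). The documents give no cost variance, R² or power for Aim 4, so both R² and the 80% starting point are assumptions.

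| Assumed R² | 0.05 | 0.10 | 0.13 | 0.20 | 0.25 |
|---|---|---|---|---|---|
| Adjusted power | 82% | 84% | 85% | 88% | 90% |

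**4. Completeness of candidate covariates.** Enrolment is 154+152+154+63 = 523. Care-receiver residence is recorded for 145+142+134+62 = 483, so 40 are missing. Diagnosis is recorded for 51+44+45+23 = 163 (31%). The table has no row for care-receiver age, so its completeness is unknown.

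**The case against.** The strongest reply is that silence is not exclusion. A reader might infer that the cost regressions left out every covariate. The documents do not say so. The Aim 4 measures section says enrolment demographics served the group comparisons, the cost analyses are called regressions, and the reference of the adjustment sentence is not beyond dispute. That stands: the supportable finding is that covariates are not specified, not that they were omitted.

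A reader might also infer that ignoring the stratum makes the cost intervals too wide. That is not shown. Only one partner agency is described and site is never defined; if it has little spread, any gain must come from other covariates. The count models are no precedent for a site term, since their sentence mentions demographics only.

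Nor is it shown that a Group 4 cost difference reflects who was enrolled. No passage links residence or gender to cost. The residence gap lies in two small categories (2 and 6 Group 4 clients); private or group home is 54/62 = 87.1% against 355/421 = 84.3% (p = 0.57).

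Larger Group 4 differences exist: bereaved 4/63 = 6.3% against 136/448 = 30.4%, and dementia diagnosis 13/23 = 56.5% against 7/140 = 5.0%. I do not rest the point on them. Patient death is recorded during participation, so bereavement may be post-baseline, and diagnosis is recorded for under a third.

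Finally, picking covariates from observed imbalance, in a document that already reports outcome results, would be data-driven. That objection is sound and shapes the fix.

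**Conclusion.** The point holds in limited form. As written, the total-cost regressions specify neither the randomisation stratum nor any baseline covariate, and this does not fit the enrolment, Aims 1 and 2, and Aim 4 measures sections.

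The precision effect is unknown: 2 points of power at an assumed R² of 0.05, 10 points at 0.25. The Group 4 case-mix differences are real and reproducible; their effect on cost is conjecture, from 0.02 to 0.18 SD per variable under the assumed cost differences.

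A reader might also conclude from the 63 clients in Group 4, and from passages that still speak of three groups, that Group 4 was not randomised alongside the others. The Design section states random assignment to four groups, and the documents do not settle the matter. If allocation was not concurrent, adjustment would reduce measured differences but would not make those contrasts randomised comparisons.

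Priority is low: Aim 4 is outside the primary analyses, and confidence in a material effect on results is low.

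**What to change.** 1. Define site, and state whether the adjustment sentence covers total cost as well as counts.
2. Fit the total-cost regressions, the Poisson models and the zero-inflated Poisson models with site and one common covariate set. Take the set from the plan's own Aim 4 enrolment list, not from observed imbalance: for example patient and caregiver age and sex, relationship and caregiver residence, plus diagnosis with a stated missing-data rule.
3. Care-receiver residence is not on that list; add it, if wanted, as a sensitivity covariate.
4. Report adjusted differences with confidence intervals alongside the unadjusted ones.
5. Say how and when Group 4 was allocated, and state that adjustment does not make its contrasts randomised comparisons if allocation was not concurrent.

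The cost is a short addition to the plan, a rerun on data the plan says were collected, a few degrees of freedom, and a missing-data rule, which matters most for diagnosis.
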